### **Verbal Fluency**

1. *Letter Verbal Fluency*: Participants produce as many words (F, A, S, or P, R, W) as they can that begin with that letter in 60 seconds. Clinical findings are in line with numerous functional magnetic resonance imaging studies, demonstrating that letter verbal fluency is associated with extensive activation in the left frontal cortex. Further, age-related decline in letter fluency have been demonstrated.

2. *Semantic Verbal Fluency*: Participants produce as many words as they can that fit a particular category (animals or fruits/vegetables) in 60 seconds. This is generally considered a measure of a verbal component of executive function and has been demonstrated to decline with age.
3. *Switching Verbal Fluency*: The switching condition evaluates the examinee's ability to generate exemplars while alternating between two different semantic categories (i.e. fruits and furniture) in 60 seconds. Switching requires the ability to engage in strategic search processes such as initiation, cognitive flexibility and mental set shifting. Because it is related to fronto-executive functioning, impaired performance is seen among patients with frontal lobe lesions and older adults.

### **Response Inhibition**

1. *Color-word Interference Test*: Participants say the color in which another color word is printed in (e.g., for BLUE printed in red ink, the answer is 'red'). This is a commonly used executive function task. Additionally, the interference effect, caused by difficulty inhibiting over-learned word reading, is often more pronounced in older adults.

### **Working Memory**

1. *Digit Span forward/backward*: Participants must recall increasingly long strings of digits in order (forward) or reverse order (backwards) of presentation. Central executive component of working memory has been demonstrated to play a key role in digit backward span performance and age-related decline has been reported.
2. *Hopkins Verbal Learning Test*: Assess verbal learning and memory (immediate recall, delayed recall, delayed recognition).
3. *Digit Symbol-Coding*: a neuropsychological test sensitive to brain damage, dementia, age and depression. It consists of digit-symbol pairs followed by a list of digits. Under each digit the subject should write down the corresponding symbol as fast as possible. The number of correct symbols within the allowed time (e.g. 90 or 120 sec) is measured.
4. *N-back task*: Both the verbal and visual working memory tasks will be evaluated in the versions of the n-back task. Versions of n-back tasks have been shown to be sensitive to working memory. During the n-back tasks, verbal or visual stimuli are shown one at a time using a laptop computer. For each stimulus, participants click the left mouse button of the computer if the stimulus is a target and the right mouse button if the stimulus is a non-target. Targets are stimuli that occur n stimuli previously (i.e., n stimuli back). For each task, 1-back, 2-back, and 3-back runs are given. Each run has 100 stimulus presentations, with 20 targets and 80 non-targets. Stimuli are presented for 500 ms with inter-stimulus intervals of 3000 ms. A 60 sec break occurs after the first 50 stimuli of each run. Both accuracy and latency of response are recorded. Verbal and visual stimuli are as follows: (1) Verbal stimuli

are common, highly imageable English words 4 to 6 letters in length. 3 stimuli are chosen from each of 3 categories (animals, tools, vehicles). Targets are trials in which an animal name is presented when an animal name is presented  $n$  stimuli back (e.g., in the following 3-back sequence, the target is in bold: “dog, horse, hammer, **cat**, car”). (2) The visual task are 9 non-sense shapes. Targets are any trial on which a shape is presented when the identical shape is presented  $n$  stimuli back.

### **Non-Verbal Executive Function**

1. *Trail Making Test A and B*: Easily administered tests measure attention, visual searching, mental processing speed, and the ability to mentally control simultaneous stimulus patterns.

### **Crystallized Word Knowledge**

1. *American National Adult Reading Test (ANART)*: reading test used to help assess intelligence.

All cognitive testing will take place in the primary laboratory of the PI at the Atlanta VA Medical Center. All evaluations will be done by the PI or appropriate study staff. Additionally, to evaluate efficacy of interventions participants will self-report on:

1. Mac-Q- 6 item questionnaire to asking participants to describe their ability to perform memory task as compared to when they were in high school.
2. Behavior Rating Inventory of Executive Function (BRIEF)- Assesses self reported impairment of executive function task related to activities of daily living.
3. Self-Efficacy for exercise scale - a 13-item instrument that measures self-efficacy barriers to exercise,
4. Epworth Sleepiness Scale- self report used to determine the level of daytime sleepiness.
5. Apathy Index (MAI)- 14 item self-report instrument that measures overall apathy and participants interest in new things.
6. Pittsburgh Sleep Quality Index- 10 item questionnaire examining participants sleep habits over the past month.
7. Patient Health Questionnaire (PHQ-9) – 9-item instrument that screens for signs and symptoms of depression.
8. Pelvic Floor Distress Inventory Questionnaire (PFDI-20) – 20 item questionnaire that screens for bowel, bladder, or pelvic symptoms.

### **Video Conferencing for Assessments**

To limit face-to-face interactions with participants, the study will be using Emory and VA-approved video or audio communication to screen and consent. Some VA-approved virtual methods include Microsoft Teams Version 1.3+, Zoom 5.0 or greater, and Cisco

WebEx version 40+. Recordings of the audio or visual communication will be permitted as described previously to facilitate scoring of the assessment data in an off-line manner. During appointment scheduling, the participant will be asked if they have access to a computer with video, microphone, and speaker capabilities with access to high-speed internet that supports this level of communication. Once equipment access is confirmed the participant will be eligible to participate in tele-assessment, instructions for accessing the tele-assessment session will be sent via encrypted email through the VA outlook server. Any test that can be administered via video should be administered at this time. If an assessment cannot be accomplished remotely, it may be administered on the day of an in-person visit.

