The fMRI acquisition for semantic will follow protocols currently utilized in the investigator's laboratory and therefore will employ a sparse-temporal sampling design in which the response is assessed in the scanner during an off-phase, and the hemodynamic response is acquired after a short time delay; thereby movement artifacts due to the articulation process are avoided. Since the working memory task involves no overt speech, a continuous sampling acquisition will be used to allow for temporal resolution of the different phases of the working memory task. A T2\*-weighted FastField Echo, Echo-Planer-Imaging (FFE-EPI) sequence utilizing a parallel imaging technique will be used. Prior to the first scan, a training session outside of the scanner will be performed to familiarize the participants with experimental tasks. Participants will be scanned prior to and following the 12-week intervention. Additionally, for fluency both semantic and phonemic stimulus presentation will be different but equalized for difficulty from pre to post.

The MRI/fMRI will be conducted at Emory University Hospital (EUH). EUH houses a 3 T Siemens Trio scanner with the total imaging matrix (TIM) suite. The scanner is equipped with a 32-channel Siemens head coil, which allows for rapid acquisition of high-resolution functional images (e.g., 2 X 2 X 2 mm voxels with a whole brain acquisition every second). It has the latest Siemens VB17 software and has a number of advanced Siemens product sequences including Blood Oxygenation Level Dependent (BOLD) imaging and in-line analysis suite with 3D PACE real time motion correction.

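### Two sections conflict on where cognitive tests are given, and nothing fixes test mode or fluency form across visits, so the paired pre-to-post tests could read a mode or form shift as change

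*Combined protocol and SAP*

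**What the plan says.** **Place of testing.** The Crystallized Word Knowledge section closes the list of cognitive tests with "All cognitive testing will take place in the primary laboratory of the PI at the Atlanta VA Medical Center". The section on Video Conferencing for Assessments opens by speaking of screening and consent but goes on to tele-assessment: "Once equipment access is confirmed the participant will be eligible to participate in tele-assessment", and then "Any test that can be administered via video should be administered at this time". The fallback is "If an assessment cannot be accomplished remotely, it may be administered on the day of an in-person visit".

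**Fluency forms.** Under Verbal Fluency, the letter test reads "Participants produce as many words (F, A, S, or P, R, W) as they can that begin with that letter in 60 seconds" and the semantic test reads "Participants produce as many words as they can that fit a particular category (animals or fruits/vegetables) in 60 seconds". Neither entry says who gets which set, or whether the set changes between visits. For the scanner version only, FMRI Tasks says "for fluency both semantic and phonemic stimulus presentation will be different but equalized for difficulty from pre to post".

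**Analysis.** Behavioral and Self-Report Data tests fluency and motor skills from pre to post by paired t-test, and adds a mixed regression whose only named factor is session. Neither has a term for mode or form. Power Analysis and Sample Size treats semantic fluency as the behavioral outcome. It uses n=44 in the Spin group with alpha 0.0261, and also considers a between-group comparison with 44 per group.

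**The concern.** Staff cannot follow both rules on where to test as they are written. In practice mode will depend on each participant's equipment and on scheduling, and a participant could be tested by video at one visit and in the laboratory at the other. If scores differ between modes, that difference enters the participant's change score. A fixed order of the two fluency lists would do the same if one list is easier.

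A paired test compares each group only with itself, so it would attribute such a shift to the intervention, in either direction. The wait-list condition does not help, because it has no cognitive testing over its waiting period and so cannot show what a repeat test without training would give. At stake are the within-group claims about fluency and other behavioral outcomes.

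**Working it through.** **Step 1: the text side by side.**

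| Question | What the documents give |
|---|---|
| Where are cognitive tests done? | All in the laboratory (Crystallized Word Knowledge); by video wherever possible (Video Conferencing for Assessments) |
| Which tests go by video? | Not listed |
| Same mode at pre and post? | Not required |
| Mode or form recorded? | Not stated |
| How are out-of-scanner fluency lists assigned? | Not stated |
| Difficulty matched from pre to post? | Stated for the scanner fluency task only |
| Order varied at random? | Stated for the walking-while-talking letters (Physical Function), not for fluency |

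**Step 2: the plan's own power figure.** Inputs from Power Analysis and Sample Size are n=44, alpha 0.0261 and d=0.5, with a stated power of 0.80. The number of sides is not given; I assume two. The paired t-test has 43 degrees of freedom, a critical value of 2.304 and a noncentrality of d × √44 = 0.5 × 6.633 = 3.317. The noncentral t distribution gives power 0.840. Power 0.80 is reached at d=0.476, which rounds to the stated 0.5, so the plan's figure is reproduced to rounding.

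**Step 3: an assumed shift with no true effect.** The documents give no size for a mode or form difference, so I take a range. If the whole group shifts by δ SD of the change score, the same formula with δ in place of d gives the chance of a significant result:

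| δ (assumed) | Noncentrality δ × 6.633 | Chance of significance |
|---|---|---|
| 0 | 0 | 2.6% |
| 0.1 | 0.663 | 5.9% |
| 0.2 | 1.327 | 17.5% |
| 0.3 | 1.990 | 38.5% |
| 0.5 | 3.317 | 84.0% |

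**Step 4: only some participants switch.** The mean shift is roughly the share who switch times the mode effect. With 20% switching and a 0.5 SD effect it is 0.20 × 0.5 = 0.1 SD, which is the 5.9% row.

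**Step 5: between-group comparison, 44 per group.** Only the difference in mean shift between arms matters; the noncentrality is that difference × √(44/2), with 86 degrees of freedom. If the shift is equal in both arms, the rate stays at 2.6%. If the share switching differs by 25 points and the mode effect is 0.3 SD, the difference is 0.25 × 0.3 = 0.075 SD and the rate is about 3.5%.

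**The case against.** **The video section may be an overlay.** It is framed as a way to limit face-to-face contact, and the protocol pairs in-person with remote routes for consent and exercise too. On that reading this is a wording slip, and the same equipment rule at each visit would keep most people in one mode. That is fair as to intent. But the laboratory rule says all testing, no sentence subordinates one rule to the other, and constancy of mode is left to chance.

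**The fluency lists may not change.** A reader might infer that the out-of-scanner forms differ from pre to post. The documents say that only of the scanner task, where difficulty is equalized. For the other tests the text offers alternatives and is silent on their use; the gap is an unspecified assignment, not a stated imbalance.

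**Most of the battery may be insensitive to mode.** A reader might also infer that the tests are mostly timed and spoken. Of the ten listed, at most four are: the three fluency tests and color-word interference, and no timing is stated for the last. That video alters scores is plausible but has no source in the documents.

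**Category overlap.** The switching test involves "alternating between two different semantic categories (i.e. fruits and furniture) in 60 seconds", and fruits also appears in a semantic list, so one might suppose that participants rehearse part of the switching test. No order of administration is given, and with the same list at both visits any carry-over would occur twice. The documents do not support that claim.

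**The exposure is confined to within-group tests.** This stands. A shift common to both arms cancels in the between-group fluency comparison that the power section considers. However, Behavioral and Self-Report Data names no such test; it names paired tests.

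**Conclusion.** The point holds as a minor one. The two sections conflict and must be reconciled. Neither mode nor fluency form is controlled across visits, and the paired t-tests would absorb any systematic shift in either.

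The size is unknown. The rates of about 6% to 84% are conditional on an assumed shift of 0.1 to 0.5 SD of the change score, shared by all 44 people in one direction, with alpha 0.0261 two-sided and no true effect. That pattern fits a fixed list order or a wholesale change of mode; partial switching gives less. The figures show how exposed the test is and do not predict what this trial will see.

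A reader might go further and infer that the trial's main results are compromised. The documents do not support this: Aims 1 and 2 rest on perfusion and CVR from imaging, which this issue does not touch, and laboratory fluency is a supporting behavioral outcome.

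**What to change.** 1. Reconcile the Crystallized Word Knowledge and Video Conferencing for Assessments sections: name the mode for each test, and keep each participant in the same mode for each test at pre and post.
2. Record mode and form for every test at every visit. If they are not captured at the time, they may be unrecoverable.
3. Under Verbal Fluency, assign the order of the alternative letter and category sets by a counterbalanced schedule within arm. The Recruitment section says these measurements are shared with two other studies, so the schedule should be agreed with them. The switching categories can stay as they are; changing them here alone could break that commonality.
4. In Behavioral and Self-Report Data, add a sensitivity analysis on participants whose mode changed.

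The cost is protocol wording, a form-order list, two extra data fields and some coordination with the sharing studies. The one practical downside is slightly tighter scheduling, since someone who starts a test by video must repeat it by video.

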### Physical Function

1. *400 Meter Walk*: Participants will be asked to walk at their usual pace, without over-exerting. They can stop for up to 1 min for fatigue or other symptoms. A time limit of 15 minutes to perform the test has been established based on the following considerations. First, individuals who complete the walk in >15 minutes have an extremely slow pace (<0.44 m/sec), which would make their walking capacity of little utility in daily life. Second, selecting a higher cut-point, such as 30 or 60 minutes makes the objective assessment impractical and does not add to the clinical significance of the outcome. Participants will be allowed to use a cane, but not a walker, to complete the 400m walk. Procedurally, we will first request that participants attempt the walk without the use of a cane. Those who feel unsafe will be allowed to attempt the walk with their cane.
2. *Walking and Walking While Talking*: Participants will be asked to walk across an electronic walkway which captures walking speed and foot placement in a quiet well-lit hallway wearing comfortable footwear. Start and stop points 10 meters apart will be marked by lines on the floor and include 3 feet from the walkway edge for initial acceleration and terminal deceleration. Eight walking trials will be randomly conducted; 4 singles tasks walking only trials and 4 dual task walking while talking trials. For the walking while talking trials participants will be asked to recite alternating letters of the alphabet. The order of the initial letter will randomly vary between “A” and “B” to minimize practice effects and/or count backwards by 3’s.
3. *Short Physical Performance Battery (SPPB)*: The SPPB is based on a timed short distance walk, repeated chair stands and a balance test (as described by Guralnik et al.). The battery will be administered by a trained and certified examiner.
4. *The Activities-specific Balance Confidence (ABC) Scale*: Indicates self-report of participants’ level of confidence in doing daily activity without losing their balance or becoming unsteady. Self-Report Function Questionnaire. We will use a

modified version of the disability instrument that was used in LIFE-P, now called the Pepper Assessment Tool for Disability (PAT-D). The questionnaire inquires about perceived difficulties in general activities of daily living during the last month. For each item, the response categories include: 1) no difficulty, 2) a little difficulty, 3) some difficulty, 4) a lot of difficulty, or 5) unable to do. Answers are averaged across the items, in order to better assess the overall perceived disability burden by a person. The questionnaire consists of 5 subscales: mobility, transferring, upper extremity, instrumental and basic ADLs. In addition to being a valid measure, the disability questionnaire has been shown to be responsive to change in previous exercise intervention studies among various disease populations.

5. *Sit and Reach Test*: This test assesses the flexibility of the lower back and hamstrings. Participants will sit on the floor and reach as far they can towards their toes. The test will be performed three times while measuring the distance reached.
6. *Functional Reach Test*: This test will assess participants' balance and functional mobility by having them stand perpendicular to a wall and reach out as far as possible.
7. *Leg Press*: An assessment of bilateral leg movement function will be completed using the Keiser Leg press.
8. To confirm the cardiovascular effect of the aerobic training participants will also perform a Maximal Treadmill Exercise Test or a Submaximal Treadmill Exercise Test.

*Submaximal Treadmill Exercise Test*: (For participants unable to complete a maximal test or if maximal testing is not indicated...) Submaximal exercise testing will be performed using an exercise protocol validated for this purpose (e.g., Naughton, modified Bruce, or similar). For graded protocols where participants progress through a series of stages in which speed, incline, or both are increased in a stepwise manner, the progression will be such that it allows the participant to adapt to a specific workload before advancing onto a more difficult stage. Termination of the test occurs if the participant requests to stop, the submaximal threshold is reached, other symptoms prohibit further exercise, or there is an absolute indication for termination of exercise testing.

*Maximal Treadmill Exercise Test*: Unless contraindicated, participants will undergo maximal exercise testing using an exercise protocol validated for this purpose (e.g., Bruce, Balke, or similar, or using a ramp protocol). Participants will progress through a gradual increase in work rate based on the specific protocol being used until they either become fatigued and decide to stop, develop other symptoms that prohibit further exercise (e.g., musculoskeletal pain), or there is an absolute indication for termination of exercise testing. Vital signs, including blood pressure

and heart rate, will be recorded at regular intervals throughout the test, and participants will be monitored with continuous electrocardiography. Participants may also be asked to report their rate of perceived exertion (RPE) at various points during the test. After testing, participants will be monitored until their heart rate and perceived exertion have normalized. A registered nurse (RN) or exercise physiologist (EP) will be present for the test duration.

9. *Electronic Activity Data:* Electronic activity data will be generated by Apple Watches functioning in two possible modes. Each mode has unique requirements for data security. The Watch will collect the participants' daily total activity level.

*Stand-alone:* Some Apple Watches loaned to participants will be paired with VA furnished iPhones. When not loaned out to participants, these iPhones will remain at the VA in a locked and secure environment (12C-173b). Because the watches will be functioning at a remote location, they will be unable to sync the data they generate to an iPhone or a network cloud. Instead, our team has written code to preserve this data in formatted files on the watch until the watch is returned to our possession. The data stored on passcode protected Apple Watches is secured with AES-256 encryption.

Once the watch is returned to the VA, it will be synced to the VA-issued iPhone. (iCloud backup will be disabled for apps handling Apple Watch generated data.) The data transferred will be devoid of participant identifiers except participant study ID, year of birth, timestamps, and Apple Watch device identifiers. It should be noted that although the timestamps contain dates, these dates are not directly related to significant life events (e.g. birth, death, hospital admission) but rather are continuously catalogued while the watches are on and not charging. Also, Apple Watch device identifiers are not perpetually unique to a participant because these watches are VA property and will be worn by numerous participants over time. Regardless, data stored on passcode-protected watches and phones will remain AES 256-bit encrypted.

Once data files are located on a VA iPhone, they will be backed up to a study controlled Apple iTunes account that is linked to a study-provided Apple User identification (UID) and transferred to a disk-encrypted, password-protected VA laptop. (Local iTunes encryption is optional by default but will be enabled for our purposes.)

*Deployed with VA-issued iPhone:* Some Apple Watches will be loaned to participants along with the iPhones to which they are paired. This mode is preferable to the Stand-alone mode; however, Stand-alone mode may be necessary if access to VA-issued iPhones is limited. Most data handling

procedures and precautions used for Stand-alone mode apply to this use-case as well, including use of participant Study ID, AES 256-bit encryption, and disabled iCloud backup. One exception is that data generated by the Apple Watch will be synced directly to the paired VA-issued iPhone (i.e. - our code writing files to the Apple Watch will not be used). The iPhones loaned to participants will not have data plans. Therefore, unless participants have Wi-Fi access, data will be retrieved from the iPhones as described for Stand-alone mode after the phones are returned to the study team (i.e. study-controlled iTunes encrypted backup, and ultimately, transfer to a VA password-protected computer). If participants have Wi-Fi access, study data will be transferred to a remote server (hosted by Emory University in a secure data center under a VA Data Usage Agreement) via SSL encrypted connections. Terms specified in the handling of research data in the Data Usage Agreement will apply.

To increase data security, de-identified user data will be encrypted using Apple's Secure Enclave coprocessor embedded in Apple's A9 series processors (in the iPhone SE and Apple Watch). A FIPS-140-2 FISMA High environment, the Secure Enclave runs the L4 microkernel which is signed by an ephemeral key and nonce entangled to the unique ID (UID) of the user with antireplay initiated at login. Antireplay revokes all data back transformation of encrypted data without express sign-on through direct passcode authentication. This means that all data is encrypted throughout transmission until authenticated by the UID on an iOS device. The encryption scheme uses a dedicated AES-256-XNT engine. No software or firmware can read this data directly. Only after decryption by the silicon based cryptographic engine using the UID key can the data be accessed, and this is further restricted to devices sharing a group id (GID). This can only be completed on another iOS device that has the UID (which is controlled by the study coordinator) and the Secure Enclave decryption engine on a device with at least an A7 series encryption coprocessor. Apple synchronizes this encrypted, de-identified data on its secure Health environment located on cloud services. These data cannot be decrypted or read by any party that does not have access to the UID, generated at the outset of the study and resides with the study staff. Only study staff can read files from the Health environment due to this encryption. Even if the physical chips are removed from the device to access the data, the device UID that created would maintain encryption of the data rendering the files inaccessible. Apple's cryptographic architecture received NIST validation as FIPS-140-2 validated with Certificate #3148 (3/8/2018 - 3/9/2023).

For all modes, filenames contain dates and times indicating when the files were created for transmission/export. These dates/times do not necessarily reflect date and times that the data were generated.

